## 1.0 Background

[figure not shown]
**A. Definition of DIH.** Various definitions have been used for intradialytic hypotension. The National Kidney Foundation Kidney Disease Outcome Quality Initiative (K/DOQI) has defined DIH as a reduction in systolic blood pressure or mean arterial pressure during hemodialysis, which it is associated with symptoms such as muscle cramps, anxiety, yawning, dizziness, fainting, or abdominal discomfort. The reduction in blood pressure should be equal to or greater than 20 mmHg for systolic blood pressure and equal to or greater than 10 mmHg for mean arterial blood pressure. Most of the reduction of blood pressure during hemodialysis occurs during the first quarter of treatment with a gradual decrease during the remaining treatment time (**Figure 1**). Some investigators use a nadir-based DIH definition—when the systolic blood pressure

falls below 90 or 100 mmHg., or the need for nursing intervention in addition to experiencing a fall in blood pressure and clinical symptoms. The reduction in blood pressure can also be asymptomatic. Thus, it is important to recognize the occurrence of repeated episodes of hypotension that will damage organs including the brain, heart, gut, and liver as well as skeletal muscle. Furthermore, it is important to identify patients who are susceptible to intradialytic hypotension to prevent the undesirable consequences of DIH.

**B. Morbidity and mortality of DIH.** Approximately 75% of patients suffer at least one episode of hypotension during hemodialysis, and DIH occurs in approximately 20 to 30% of all regular hemodialysis treatments. DIH is a common clinical complication of hemodialysis, and it is associated with increased morbidity and mortality. It has been shown that DIH may induce myocardial dysfunction due to reduced myocardial blood flow. Recurrent episodes of hypotension are also associated with frontal lobe atrophy in the brain, and with mesenteric ischemia. Previous studies have identified an association between DIH and cardiovascular morbidity-mortality, and all-cause mortality. Two more recent studies, using large databases, also showed the association between DIH and mortality.

Nursing interventions during hemodialysis are usually initiated by patient-reported symptoms. Among them, nausea, dizziness, cramps, and fatigue are common during hemodialysis. DIH is associated with some of these symptoms, particularly dizziness and cramps. Furthermore, DIH and a higher ultrafiltration rate have been associated with longer hemodialysis recovery time, a measure of the quality of life (QOL) that has been validated in patients on hemodialysis that correlates well with longer and more complex QOL questionnaires.

**C. Multiple factors contribute to the pathophysiology of DIH.** The pathogenesis of DIH and intradialytic hypotension have been attributed to the rapid removal of plasma volume during hemodialysis, a high rate of ultrafiltration and the inadequate mechanisms

**Figure 1.** Blood pressure reduction during hemodialysis

to respond to hypovolemia in patients with ESRD. Thus, the occurrence of DIH would depend on the rate of fluid removal and the compensatory mechanism for refilling the plasma volume (**Figure 2**). The rate of fluid removal can be controlled by limiting the ultrafiltration rate or increasing the hemodialysis time. Conversely, the compensatory mechanisms to hypovolemia are more difficult to control, and they depend on the patient's comorbidities—such as impaired cardiac contractility, reduced cardiac reserve, autonomic dysfunction, and reduced venous compliance. Cardiac compensations include increasing the heart rate and the contractility. Venous tone is also an important compensatory mechanism since more than three liters of plasma volume is located within the veins. The increase of arteriolar vasoconstriction is another normal response to hypovolemia and hypotension. Thus, it has been proposed that patients with DIH have impaired compensatory mechanisms.

The autonomic nervous system controls many of the compensatory mechanisms to hypovolemia, such as heart rate, venous compliance, and arteriolar tone. Thus, it has been proposed that autonomic dysfunction plays a major role in DIH. In fact, although patients on hemodialysis frequently present with dysfunction of the autonomic nervous system, the real prevalence in this population is unknown. Due to fluid removal, hemodialysis activates the sympathetic nervous system; thus, inappropriate activation of this system contributes to DIH.

The lack of vasoconstriction in response to hypovolemia has been implicated as one of the impaired responses during DIH. This may be due to the removal of vasoconstrictors or the increased production of vasodilators. Vasopressin, a vasoactive peptide that increases during hypovolemia, seems to have a blunted response during hemodialysis in patients with DIH. Nitric oxide, another potent vasodilator, has been found elevated in patients with DIH. Adenosine has also been implicated in the occurrence of DIH through the inhibitory effect on norepinephrine release.

Besides, hypo-perfused tissues may release adenosine that may have a local effect on vasodilation, which may worsen blood pressure reduction. Accordingly, a recent study showed that blocking adenosine A1 receptor may improve DIH. Bradykinin is another vasoactive substance that is released during hypoperfusion and may have a role in the pathogenesis of DIH. It is noteworthy to mention that bradykinin may also act locally by stimulating cardiac vagal afferent chemoreceptors leading to sympathetic inhibition.

[figure not shown]

Figure 2. Factors associated with dialysis-induced hypotension (DIH)

**D. Activation of the kallikrein-kinin system during hemodialysis increases bradykinin and may contribute hypotension.** Bradykinin, a potent vasoactive peptide, results from the cleavage of high molecular kininogen (HMWK) by tissue and plasma kallikreins. Bradykinin induces vasodilation by stimulation of the bradykinin B2 receptor. Hemodialysis induces the activation of the kallikrein-kinin system and the

[figure not shown]
production of bradykinin. During hemodialysis, contact of blood with the dialyzer also activates the contact system, which in turn also increases bradykinin levels. Bradykinin levels are also increased during cardiopulmonary bypass, and one of the complications of cardiopulmonary bypass is protamine-induced hypotension. Our group has previously shown that the hypotensive events coincide with increased levels of bradykinin. Furthermore, blocking the bradykinin B2 receptor with icatibant attenuates the hypotensive response to protamine. Thus, bradykinin may also induce hypotension during hemodialysis by inducing vasodilation. We have previously reported that bradykinin B2 receptor blockade does not affect blood pressure reduction during hemodialysis, but we did not assess the contribution of bradykinin to DIH. A novel therapeutic alternative to inhibit the activation of the kallikrein-kinin system is lanadelumab, a human monoclonal antibody against plasma kallikrein, that prevents the cleavage of H&WK and the subsequent increase in bradykinin. Lanadelumab is an FDA approved drug against hereditary angioedema; however, the role of lanadelumab on dialysis induced hypotension has not been explored.

## 2.0 Rationale and Specific Aims

### A. Specific Aims

In **Specific Aim 1** we will test the hypothesis that **in patients with DIH, inhibition of plasma kallikrein system with lanadelumab prevents the reduction of blood pressure and maintains hemodynamic stability**. For this purpose, we will monitor heart rate and blood pressure during hemodialysis. Importantly, we will conduct the study in an outpatient clinic, using the patients' usual hemodialysis dose and settings as for a regular hemodialysis session. This approach will minimize the risk that our findings were biased by conducting the study in a clinical research setting.

In **Specific Aim 2** we will test the hypothesis that **in patients with DIH, inhibition of plasma kallikrein system with lanadelumab prevents symptoms associated with DIH such as cramps, dizziness, and nausea and improve recovery time after hemodialysis**. Hemodialysis is associated with many complications, including DIH, that negatively affect the QOL of patients and their families. Any intervention that prevents the occurrence of DIH will result in a faster recovery from hemodialysis. The present study will evaluate the impact of lanadelumab on preventing symptoms associated with DIH and reducing recovery time after hemodialysis.

**Figure 3.** Effect of one- week treatment with ramipril or placebo on bradykinin concentrations in response to hemodialysis

[figure not shown]
## 3.0 PRELIMINARY RESULTS

### Bradykinin increases during hemodialysis

Hemodialysis activates the kallikrein-kinin system and increases the levels of bradykinin. Accordingly, we have previously shown that bradykinin levels increase during the first 30 minutes of hemodialysis in 15 subjects that received 5 mg of ramipril for seven days (**Figure 3**).

## Bradykinin B2 receptor blockade prevents an excessive decrease in blood pressure

Another method for evaluating the effects of bradykinin during hemodialysis is by blocking its receptor. Thus, we evaluated the effect of icatibant on blood pressure during hemodialysis. For this purpose, we performed a secondary analysis in a randomized, double-blind, placebo-controlled study designed to examine the effect of icatibant on mitochondrial function during hemodialysis ([NCT03177798](#)). Icatibant or placebo was continuously IV-infused 30 minutes before the initiation of hemodialysis and throughout the whole hemodialysis session. Icatibant was infused at a dose of 100 ug/kg/h before hemodialysis, which was then changed to 50 ug/kg/h for the duration of hemodialysis. As we previously reported, we found that icatibant has no overall effect on blood pressure or heart rate during hemodialysis. We then stratified the analysis based on a reduction of systolic blood pressure (SBP) equal to or greater than 20 mmHg during hemodialysis. We found that in those patients with a reduction in blood pressure, icatibant prevented the decrease in SBP compared to placebo (**Figure 4A-B**). We also found that icatibant blunted the rise in heart rate during hemodialysis in patients whose blood pressure reduction was equal to or greater than 20 mmHg (**Figure 4C**). Icatibant did not affect either blood pressure or heart rate in patients who did not have a significant blood pressure reduction during hemodialysis.

**Figure 4.** Effect of icatibant on blood pressure and heart rate during hemodialysis in patients with a reduction of blood pressure  $\geq 20$  mmHg (n=7).

## 4.0 Inclusion/Exclusion Criteria

### Study population

Participants will be recruited from Vanderbilt Dialysis Outpatient Clinics. We will enroll patients who are on maintenance hemodialysis for at least six months, with pre-dialysis blood pressure between 110 and 170 mmHg, who are being adequately dialyzed ( $Kt/V > 1.2$ ), and who are between 18 and 85 years old, who have experienced dialysis-induced hypotension (DIH) episodes at least four times in a period of 12 weeks prior to enrollment. We define DIH as the drop of systolic blood pressure (SBP) of more than 30 mmHg with associated symptoms such as nausea, dizziness, cramps, yawning, and abdominal discomfort. We will also look for nursing intervention during the hypotensive episode, but it will not be used as an inclusion criterion. Nursing intervention is defined as a temporary interruption of ultrafiltration, Trendelenburg positioning, or administration of intravenous fluids. We will exclude patients who suffered severe DIH episodes that required the use of vasopressors and the termination of hemodialysis treatment. Patients who have been hospitalized during the last three months or with clinical evidence of inflammatory or infectious disease or with severe anemia (hemoglobin less than 8 g/dl) will be excluded. Institutional review board approval and written informed consent will be

obtained from all study subjects. We expect that 60% of our subjects will be African American and 40% will be women.

*Inclusion criteria*

- Subjects age 18 to 85 years
- On thrice-weekly hemodialysis for at least six months
- Clinically stable, adequately dialyzed (single-pool Kt/V > 1.2), with polysulphone membrane for at least three consecutive months before the study
- Subjects with pre-dialytic systolic blood pressure between 110 and 170 mmHg.
- Subjects with a reduction of systolic blood pressure during hemodialysis equal to or greater than 30 mmHg, with associated symptoms such as nausea, vomiting, muscle cramps, dizziness, or anxiety.
- Hypotensive episodes should occur four times or more in four weeks (12 hemodialysis sessions).

*Exclusion criteria*

- Subjects with intradialytic hypotension that require the use of pharmacological intervention such as midodrine or vasopressin
- Subjects with pre-dialytic systolic blood pressure greater than 170 mmHg or diastolic blood pressure greater than 110 mmHg
- History of myocardial infarction or cerebrovascular event within 3 months
- History of serious hemorrhage (including cerebral hemorrhage) in the past 12 months
- INR outside of the therapeutic range in the last 6 months before enrollment
- Advanced liver disease
- Ejection fraction less than 30%
- Anticipated live donor kidney transplant
- History of poor adherence to hemodialysis or medical regimen
- Severe anemia (hemoglobin less than 8 g/dl) requiring blood transfusions
- Use of immunosuppressive drugs within one month before study enrollment
- Active connective tissue disease
- History of acute infections disease within one month before study enrollment
- Inability to provide consent
- Pregnancy

## **5.0 Enrollment/Randomization**

This is a parallel study where participants will be assigned to either taking the study drug (lanadelumab) or taking the placebo (saline pre-filled syringes.) Patients will be randomly assigned to the treatment order using a permuted-block randomization algorithm. The study drug, lanadelumab, will be shipped from Takeda as pre-filled syringes along with matching placebo, also in prefilled syringes. The Vanderbilt Investigational Drug Services (IDS) will be responsible for the storage, preparation, dispensing, and labeling of the investigational agents. The Vanderbilt IDS will also maintain accurate drug storage and dispensing logs. Subjects will be randomized to receive a placebo or 300 mg of lanadelumab (Takeda Pharmaceutical, Cambridge, MA). Subjects randomized who do

not complete the whole protocol for any reason will be replaced, and their data will be analyzed separately. The half-life of lanadelumab is 14 days, and the time to reach maximum concentration is five days. For this reason, we will monitor blood pressure and the occurrence of DIH for three weeks after the administration of the second dose of the study drug.

[figure not shown]

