The next two consecutive dialysis treatments after each drug administration (days 1 and 3, and days 15 and 17), we will conduct follow-up visits at the dialysis unit to collect information regarding symptoms after discharge from the CRC. During these visits, at the end of every hemodialysis session, we will also inquire, through a standardized questionnaire, about the presence of any symptoms associated with hypotension. This questionnaire will include symptoms such as cramps, dizziness, nausea, and will be scored according to the severity from 0 to 4 (none to severe). We will also collect blood samples at the dialysis unit for pharmacokinetics and special laboratory analysis. During the six-week length of the study, we will monitor the occurrence of DIH episodes and changes in blood pressure in every dialysis session. For this purpose, we will use the dialysis clinic blood pressure monitor logs. We will also conduct two additional visits at the dialysis units (Day 29 and 43) to draw blood, administer the symptomatology questionnaire, and measure blood flow with NIRS. In the final hemodialysis visit (day 43) we will also give the patients an activity monitor that will be collected after five consecutive days of continuous use. During this last visit, we will also administer the QOL questionnaire, obtain the dialysis recovery time, and perform body composition and physical performance tests (except for the six-minute walk test). Details of the study protocol can be found in Figure 5, Tables 1 and 2, and Appendix 1

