## **8.0 Reporting of Adverse Events or Unanticipated Problems involving Risk to Participants or Others**

### **Protection against risk**

- Investigators will obtain a detailed medical history to look for the exclusion and inclusion criteria. Patients will also undergo a complete physical examination prior to being included in the study. The assessment will include a thoughtful evaluation of the cardiovascular system, including blood pressure.
- Patients will be monitored for the presence of Type I hypersensitivity reaction after the administration of the first study drug. For this purpose, the patient will remain in the CRC for two hours after the administration of the study. If the patient presents this type of reaction, proper treatment will be administered in the CRC. Also, the patient will not receive the second dose of the study drug and will be withdrawn from the study.
- Baseline laboratory analysis and metabolic panels will be obtained to screen for any hematological or biochemistry abnormality.
- A resting electrocardiogram (ECG) will be obtained during the CRC visits to look for the presence of abnormal ST segments, T-wave inversion, or cardiac arrhythmias.
- Diagnosis of myocardial infarction will require the presence of at least two of the following criteria: typical chest pain with or without radiation, electrocardiogram compatible with myocardial infarction, and elevation of cardiac enzymes (creatinine kinase MB or troponin). Stroke will be defined as new and sudden onset of neurological deficits that lasts longer than 24 hours.
- We will review blood pressures obtained at the dialysis center. If at any time the pre-dialysis systolic blood pressure exceeds 189 mmHg or diastolic blood pressure exceeds 114 mmHg, blood pressure will be closely monitored. In the case of uncontrolled high blood pressure, subjects will be discontinued from the study.
- A serum **pregnancy test** will be obtained the day of the study drug administration in all women with childbearing potential to exclude pregnancy.

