## **10.0 Statistical Considerations**

### ***a. Sample size***

The primary outcome will be the change in blood pressure during hemodialysis. For this, we will average blood pressure during hemodialysis of three hemodialysis sessions within the second week of treatment. Secondary endpoints will also be recorded during the second week of treatment and will include the number of hypotensive events, frequency of nursing interventions, average of dialysis recovery times, and average symptoms severity score. Based on our preliminary studies with icatibant and assuming a standard deviation of differences of 13.6 mmHg (pooled SD of the delta), a sample size of 16 in each arm will have 80% power to detect a difference in means of -13.7 mmHg, using a paired t-test with a 0.05 two-sided significance level.

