### ***b. Data analysis plan***

Standard graphing and screening techniques will be used to detect outliers and to ensure data accuracy. Distributions of the continuous outcomes will be assessed for normality. If normality is violated, proper data transformation will be applied, or non-parametric analysis methods will be considered. The primary endpoints are SBP and DBP. The secondary endpoints include heart rate, and the R-R interval (autonomic function), the time to recover after HD, symptoms associated with DIH, and the distance walked during the six-minute walk test.

Mixed effect models will be used to analyze the primary endpoint (blood pressure) with a random subject effect and with the treatment (lanadelumab vs placebo) and the time trend (measurements every 15 minutes) as fixed effects. The focus of this study will be the treatment effect and the time trend of the endpoints; however, mixed effect models also provide the flexibility of controlling for and evaluating covariates. However, we will be careful not to over-fitting the model due to the limited sample size.

Besides the above evaluation of the treatment effect and the time trend through the regression models, the direct treatment effect will also be estimated as within-subject mean difference along with their 95% confidence intervals. For the secondary endpoints, a paired t-test will be performed (lanadelumab vs placebo). If the normality of the data is violated, we will use non-parametric tests.

For binary endpoints (e.g., occurrence of hypotensive events), we will use the McNemar test to compare lanadelumab and placebo.

**Missing Data.** Based on our previous studies, we anticipate a drop-out rate of 10% or less. Subjects who drop out will be replaced. Specific inferences on effects of interest will be made by reporting a point estimate along with a 95% confidence interval and the p-value. Hypotheses will be tested at the level of  $\alpha=0.05$ . We will use SPSS (version 25.0, SPSS, Chicago, IL) and the open-source statistical package R (R Core Team, 2017) for analyses.

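### Randomized patients who do not complete the protocol are replaced and analyzed apart, so the main comparison excludes patients for events after randomization

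*Combined protocol and SAP*

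**What the plan says.** Section 5.0 states that randomized subjects who do "not complete the whole protocol for any reason will be replaced, and their data will be analyzed separately". Under Missing Data, Section 10.0 b gives the expectation that "we anticipate a drop-out rate of 10% or less" and the rule "Subjects who drop out will be replaced". It gives no other missing-data method. No section names an analysis population.

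Several post-randomization events end participation:

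- a hypersensitivity reaction, after which "the patient will not receive the second dose of the study drug and will be withdrawn from the study" (Section 8.0, Protection against risk);
- a transaminase rise, raised potassium, or uncontrolled high blood pressure (same section);
- a non-transient adverse event, intolerance of the first dose, or non-compliance in the investigator's opinion (Section 9.0).

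The primary outcome is taken early: "we will average blood pressure during hemodialysis of three hemodialysis sessions within the second week of treatment" (Section 10.0 a). The whole protocol is longer, and its end is described in two ways. Section 5.0 says "we will monitor blood pressure and the occurrence of DIH for three weeks after the administration of the second dose of the study drug", which is about Day 14 + 21 = Day 35. Section 6.0 says "During the six-week length of the study, we will monitor the occurrence of DIH episodes and changes in blood pressure in every dialysis session", and Appendix A schedules visits to Day 43.

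**The concern.** Randomization makes the two arms comparable at entry. Removing patients for what happens afterwards gives that up, and enrolling someone else in their place restores a count but not comparability. Blinding limits discretionary withdrawal that favours one arm. It does not prevent withdrawal caused by the drug.

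Three features make this more than a formality:

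- **Exits can differ by arm.** Hypersensitivity, first-dose intolerance and transaminase rise are possible drug effects. Whether they relate to blood pressure change is not stated.
- **Good primary data can be set aside.** The outcome window is the second week, but the rule depends on completing the whole protocol, which is not defined. If a missed late visit counts as non-completion, a patient with all three primary sessions leaves the main comparison.
- **The replacement's arm is not specified.** Assignment is made "using a permuted-block randomization algorithm". A new patient on that list need not fall in the leaver's arm, so replacement may not bring both arms back to 16.

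Analyzing leavers separately keeps their data visible, but outside the treatment comparison.

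**Working it through.** **Inputs.** From Section 10.0 a: SD 13.6 mmHg, target difference 13.7 mmHg, 16 per arm, two-sided 5% level, 80% power. From Section 10.0 b: drop-out of 10% or less, so 0.10 × 32 = 3.2, about 3 patients. Not given, and therefore assumed: which arm patients leave from, and how leaving relates to blood pressure change.

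**The plan's own figure.** With the two-sample normal approximation, n per arm = 2(1.96 + 0.842)² × 13.6² / 13.7² = 15.5, rounded up to 16, as stated. A two-sample t-test has 78.7% power at 16 per arm. The plan names a paired test, but its figure fits a two-sample comparison, so a two-sample test is used below.

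**Simple formula.** Let f be the share of an arm excluded and D the mean of the excluded minus the mean of the completers. Leaving them out shifts that arm's mean by −f × D. With 10% excluded from one arm only:

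- D = 1 SD: 0.10 × 13.6 = 1.4 mmHg, or 10% of 13.7; rejection rate under no effect 5.9%.
- D = 2 SD: 0.10 × 27.2 = 2.7 mmHg, or 20% of 13.7; rejection rate 8.5%. If the bias points toward no effect, power at 16 per arm falls from 78.7% to 59.9%.

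With 10% excluded from both arms, the shift is zero if D is the same in each. It is 2.7 to 5.4 mmHg if the D values are opposite in sign.

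**Simulation.** One normal outcome per patient, SD 13.6, no true effect, pooled two-sample t-test, 400,000 repetitions per scenario. Patients leave in order of a score that has correlation r with the outcome; r = 1 means the most extreme patients leave. Entries are shift in mmHg / type I error.

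| Scenario | r = 0 | r = 0.3 | r = 0.5 | r = 1 |
|---|---|---|---|---|
| 2 of 18 leave one arm, 16 in the other | 0 / 5.0% | 0.8 / 5.5% | 1.4 / 6.2% | 2.7 / 10.3% |
| 3 of 19 leave one arm, 16 in the other | 0 / 5.0% | 1.1 / 5.7% | 1.8 / 7.0% | 3.7 / 14.5% |
| 2 of 18 and 1 of 17 leave, opposite directions | 0 / 5.0% | 1.3 / 5.9% | 2.1 / 7.8% | 4.2 / 18.4% |
| 2 of 18 and 1 of 17 leave, same direction | 0 / 5.0% | 0.4 / 5.2% | 0.6 / 5.6% | 1.2 / 8.2% |
| 3 of 16 leave one arm, not refilled | 0 / 5.0% | 1.3 / 5.7% | 2.1 / 7.3% | 4.2 / 15.4% |
| 2 of 16 and 1 of 16 leave, opposite, not refilled | 0 / 5.0% | 1.4 / 6.0% | 2.3 / 7.8% | 4.6 / 19.2% |

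As shares of the target, 3.7/13.7 = 27% and 4.2/13.7 = 31%. Either sign is possible.

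**Timing.** The second week of treatment is not given in study days. If it means about Days 8 to 14, it ends as the second dose falls due on Day 14. A patient excluded shortly before that dose could then already have primary data. Appendix A places clinical labs on Day 13; if they include transaminases, an exclusion based on them would come at the end of that window.

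**The case against.** The strongest case against is about severity and mechanism. The text says analyzed separately, not excluded, and the mixed model in Section 10.0 b is not restricted to completers. Exits that differ by arm do not bias the result on their own; leaving must also relate to blood pressure change, and no section shows such a link. The blood pressure trigger in Section 8.0 concerns pre-dialysis pressure (above 189 systolic or 114 diastolic) and leads first to closer monitoring. The outcome is the change during dialysis. The larger error rates need r = 1. The simulation uses one value per patient, not the planned model of 15-minute readings.

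Much of this stands as a limit on size. The link to outcome is unproven, the error rates are illustrative, and r = 1 is an extreme. It does not remove the point. With replacement prescribed and no all-randomized analysis anywhere, exclusion from the main comparison is the plain reading; if the sponsor means something else, the plan has to say so. Nor do the documents rule out a link, and the 10% is an expectation, not a cap. The remarks on Day 13 labs and on allocation of replacements are conditional, and the conclusion does not need them.

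One further objection stands: if the window is about Days 8 to 14, a patient withdrawn before the second dose has had the same dosing in that window as completers. Assuming that such a patient gets no benefit is therefore a worst case.

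**Conclusion.** The concern holds, and the rule should be corrected before analysis. As written, membership of the primary comparison depends on events after randomization, and usable primary data can be discarded. The bias is probably modest at the expected drop-out: zero if leaving is unrelated to blood pressure change, 0.4 to 2.1 mmHg with 5 to 8% error at correlations of 0.3 to 0.5 when arms are refilled (up to 2.3 mmHg when they are not). The extreme cases listed reach 3.7 to 4.6 mmHg and 14 to 19%. These are assumed scenarios, not bounds. The seriousness rests on the rule being wrong for the primary comparison and cheap to correct, not on a demonstrated large bias. It matters to settle this early: Section 9.0 follows withdrawn subjects only until symptoms resolve, so outcome data not collected then may be lost.

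**What to change.** **Sections 5.0 and 10.0 b.** Delete the separate analysis of non-completers and state: *The primary comparison includes all randomized patients in their assigned arm, using blood pressure from the primary-window sessions, whether or not they complete the protocol or receive both doses.* Define the primary window in study days, reconcile the Day 35 and Day 43 descriptions, and say what counts as completing the protocol.

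**Patients with no blood pressure in the window.** Count and report them by arm. Cover them with a sensitivity analysis, for example imputing their change from the placebo arm and then shifting it over a pre-stated range. Report completers only as a further sensitivity analysis.

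**Section 9.0.** State that routine clinic-log blood pressure and hypotension data continue to be extracted through Day 43 after study drug stops, unless consent is withdrawn. The clinical withdrawal rules are unchanged.

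**Numbers.** Randomize any extra patients from the same list, in addition to those who left and not in their place. Allowing for 10% drop-out, 16/0.9 = 17.8, so 18 per arm.

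**Cost.** Mostly wording, since log review is already planned for every session. Log readings may be less frequent than every 15 minutes, so time should enter the model as actual minutes. The statistical cost is dilution:

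- If 2 of 18 lanadelumab patients get no benefit, the expected difference is 13.7 × 16/18 = 12.2 mmHg. Power with 18 per arm falls from 84% to about 72–74%; with half the benefit it is about 79%.
- If 3 of 19 get none, against 16 on placebo, it is 13.7 × 16/19 = 11.5 mmHg. Power falls from 82% to about 65–68%; with half the benefit it is 75–76%.

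For reference, 16 completers per arm give 79%. In each range the lower figure treats the arm as a mixture and the higher holds the SD at 13.6.
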